10.6.4.2. Blood Pressure Endpoints

Blood Pressure Endpoints

Pre- and Post- Dialysis BP

- For subjects undergoing dialysis in-clinic, both pre- and post- dialysis BP values will be measured.
- Unless otherwise specified, for summaries and analyses of BP values, the post-dialysis BP values for subjects undergoing dialysis in-clinic will be used.

End of Treatment BP Value

• See Section 10.6.1

Mean Arterial Pressure (MAP)

• MAP = [(2*DBP) + SBP]/3

Blood Pressure Exacerbations

- BP exacerbations will be defined as (≥ 25 mmHg increase from baseline or SBP ≥ 180 mmHg or DBP ≥ 15 mmHg increase from baseline or DBP ≥ 110 mmHg) and grouped by type as follows:
 - BP exacerbations
 - SBP exacerbations
 - \geq 25 mmHg increase from baseline or
 - SBP \geq 180 mmHg
 - $\circ \quad SBP \geq 180 \text{ mmHg and baseline SBP < 180 mmHg} \\ (including subjects with a missing baseline SBP)$
 - SBP \ge 180 mmHg and baseline SBP \ge 180 mmHg
 - DBP exacerbations
 - \geq 15 mmHg increase from baseline or
 - DBP \geq 110 mmHg
 - \circ DBP \geq 110 mmHg and baseline DBP < 110 mmHg (including subjects with a missing baseline DBP)
 - DBP \ge 110 mmHg and baseline DBP \ge 110 mmHg

Notes:

- BP values used to assess BP exacerbations must be on-treatment (see Section 10.4.1), unless otherwise specified.
- BP values used to assess BP exacerbations can be scheduled or unscheduled.
- For visits where BP is measured in triplicate, the average of the 3 BP values will be used to assess BP exacerbations.
- For subjects who have in-clinic dialysis, BP exacerbations identified using post-dialysis BP

DI	ad Proceura Endpointe
ыс	ood Pressure Endpoints
	values will be used in summaries and analyses of BP exacerbations, unless otherwise specified.
•	Subjects with multiple exacerbation events on the same calendar date for each type defined above are considered to have one exacerbation event for event counts by type. For example, a subject with an SBP and a DBP exacerbation on the same date would count in each of the SBP and DBP types, but would only count as one BP exacerbation event in in the total BP exacerbation type.
Blo	ood Pressure Exacerbation Event Date
•	Date of BP exacerbation
On	-Treatment BP Medication
٠	See Section 10.4.1 for treatment states for concomitant medications.
Ge	neral
٠	Censored time (days) = last non-zero dose date- treatment start date + 1
•	BP exacerbation person years = (cumulative total of censoring time for all subjects) / 365.25 BP exacerbation event incidence rate (per 100 person years) = (100 * number of BP exacerbations) / BP exacerbation person years
Ch	anges in Blood Pressure Medications
	• No change: no new anti-hypertensive records since baseline (day before randomized treatment start date) and no change to anti-hypertensive records since baseline until date of visit while on randomized treatment.
	 Increase: addition of new anti-hypertensive records for any reason or a change with a primary reason for changing dose/frequency or stopping of 'increased to' since baseline until date of visit while on randomized treatment
	• Decrease: discontinuation of an anti-hypertensive record with primary reason for change starting with "discontinued" or a change with a reason of 'Decreased due to…' since baseline until date of visit while on randomized treatment
	• Switch = change with a reason of 'switched to another agent' since baseline until date of visit while on randomized treatment
Cu	mulative Changes in Blood Pressure Medications
	 For the summary of cumulative changes excluding "Once only" and "PRN" records, cumulative change will be counted from the date of first randomized treatment to the Week 52 visit date while on randomized treatment. If a new anti-hypertensive medication is added during this time, it will be counted as one change. If the medication also stops during this period, then it will count as two changes (one change due to starting, and one change due to stopping). The cumulative number of changes will be calculated by adding up the changes for all records during this time period. The same steps will be repeated for the period starting from the date of first randomized treatment to End of Treatment For the summary of cumulative changes for "Once only" records only, cumulative change
	will be counted from the date of first randomized treatment to the Week 52 visit date while on randomized treatment. Since "Once only" doses will have same start and stop dates, a new anti-hypertensive medication record during this period will be counted as one change. As "once only" doses are likely administered to control BP during dialysis, so they are considered part of a single titration regimen, hence multiple "once only" records on the same date will be counted as one change. The same steps will be repeated for the period

200807

Blood Pressure Endpoints	
starting from the date of first randomized treatment to End of Treatment	

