- The models will include factors for treatment, time, prognostic randomization stratification factors (see Section 10.10.2), baseline BP parameter and the baseline BP parameter by time and treatment by time interaction terms. Analyses will be done with the MIXED procedure in SAS, using the Kenward-Roger option to estimate denominator degrees of freedom and standard errors. For analyses using on- and off-treatment values, subjects who withdraw from the study before Week 52 are considered to be missing at random and in the analysis using on-treatment values only, subjects who permanently discontinue randomized treatment before Week 52 are assumed to be missing at random.
- The difference in change from baseline in BP (SBP, DBP, and MAP) at the derived end of treatment (see Section 10.6.4) will be analyzed with an ANCOVA model including terms for treatment, prognostic randomization stratification factors (see Section 10.10.2) and the corresponding baseline BP parameter. This analysis will be performed using on-treatment BP values only.

200807

Sec	ondary Safety Statistical Analyses: Blood Pressure
•	The number of on-treatment BP exacerbation events per 100 patient years will be calculated (see Section 10.6.4). Confidence intervals for the rate per 100 patient years will also be reported. For within group rates and the ratio of model estimated exacerbation rates, the point estimates. two-sided 95% confidence intervals, and one-sided p-value for the treatment group comparison will be obtained using a negative binomial model with treatment and the prognostic randomization strata as covariates and the logarithm of time on-treatment as an offset variable.
Мо	del Results Presentation
	BP parameter values (SBP, DBP, and MAP) will be summarized using mean, standard deviation, minimum, P25, median, P75, and maximum at each visit by treatment group. In addition to scheduled visits, the derived baseline value and end of treatment values will be summarized (see Section 10.6.4). Summaries of on-treatment BP values only and on- and off-treatment BP values together will be produced. A summary of on-treatment BP values by baseline dialysis type will be produced. On-treatment BP parameter values will be plotted by visit using a line plot. BP parameter change from baseline values (SBP, DBP, and MAP) will be summarized using

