Category	Covariates and / or Subgroups	Summary of Demographics & Baseline Characteristics Note: Include 'Missing' categories, if applicable.	Subgroup Analysis for Co-primary MACE & Principal Secondary Safety Endpoints Note: Do not include 'Missing' categories.	Subgroup Analysis for Co-primary Hgb & Principal Secondary Efficacy Endpoints Note: Do not include 'Missing' categories.
	IV and other iron use only Oral and other iron use only IV, oral and other iron use			
Standardized baseline IV iron dose (mg/month)	Continuous covariate for monthly IV iron dose analysis, summary statistics of continuous values	Yes	No	No
Standardized baseline IV iron dose (mg/month) for subjects using IV iron at baseline	Continuous covariate for monthly IV iron dose analysis, summary statistics of continuous values	Yes	No	No
Baseline post-dialysis SBP (mmHg)	Continuous covariate for change from baseline in SBP analysis, summary statistics of continuous values	Yes	No	No
Baseline post-dialysis DBP (mmHg)	Continuous covariate for change from baseline in DBP analysis, summary statistics of continuous values	Yes	No	No
Baseline post-dialysis MAP (mmHg)	Continuous covariate for change from baseline in MAP analysis, summary statistics of continuous values	Yes	No	No
Dialysis access type used at randomization	Arteriovenous fistula Arteriovenous graft Central venous catheter – tunneled Central venous catheter – non-	Yes	No	No

Category	Covariates and / or Subgroups	Summary of Demographics & Baseline Characteristics Note: Include 'Missing' categories, if applicable.	Subgroup Analysis for Co-primary MACE & Principal Secondary Safety Endpoints Note: Do not include 'Missing' categories.	Subgroup Analysis for Co-primary Hgb & Principal Secondary Efficacy Endpoints Note: Do not include 'Missing' categories.
	tunneled Peritoneal catheter Other Missing			
ACEI/ARB use at randomization	No, Yes	Yes	Yes	Yes
Phosphate binder use at randomization	Iron-based phosphate binders Calcium-based phosphate binders Non-calcium and non-iron based phosphate binders No phosphate binder use	Yes	No	No
Vitamin D use at randomization	No, Yes	Yes	No	No
Baseline Kt/V urea for HD subjects	Summary statistics of continuous values	Yes	No	No
Baseline Kt/V urea for PD subjects	Summary statistics of continuous values	Yes	No	No
Baseline URR for HD subjects (%)	Summary statistics of continuous values	Yes	No	No
History of cardiovascular disease	No, Yes	Yes	Yes	No
Beta blockers use at	No, Yes	Yes	No	No

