10.14.1.4. Statistical Hypothesis

The primary sub-study estimand is to compare the treatment effect on change from baseline in 24-hour average SBP at end of sub-study, in all randomized sub-study subjects with evaluable ABPM assessments at both baseline and end of sub-study (effectiveness estimand). The statistical model for analysis will be an ANCOVA with terms for treatment and baseline 24-hour average SBP. This model will provide a point estimate and two-sided 95% CI for the treatment effect and a one-sided p-value for the superiority assessment. The primary analysis population will be the ABPM ITT population defined in Section 10.14.3, and subjects' randomized medication will be used for this analysis.

The statistical hypotheses are as follows:

Null: The difference between treatment groups (Dapro – rhEPO) in change from baseline in 24-hour average SBP at end of sub-study is ≥ 0 .

Alternative: The difference between treatment groups (Dapro - rhEPO) in change from baseline in 24-hour average SBP at end of sub-study is less than 0.

ABPM measurements are only collected once post randomization, and it is expected that approximately 20% of subjects will have missing end of sub-study ABPM data. To assess the impact of missing data on the interpretation of the primary analysis, the reason for missing data will be assessed. If the majority (> 70%) of missing data is due to either patient unwillingness to repeat the ABPM procedure or due to an un-evaluable reading, then the data will be considered to be missing at random and no adjustment will be made to the primary analysis.

If more than 30% of the data is missing for other reasons, then multiple imputation will be used for subjects with data missing due to these reasons. Regardless of randomized treatment group, this data will be imputed using the distribution of non-missing rhEPO subject data. There will be no imputation for subjects with data missing due to either patient unwillingness to repeat the ABPM procedure or due to an un-evaluable reading. This is in keeping with the primary interest in the effectiveness estimand.

The efficacy estimand is also of interest, so the primary analysis will be repeated with the ABPM Per-Protocol population using actual treatment received. Missing data will not be imputed for this analysis.

The originally-planned statistical hypotheses described above will no longer be tested.

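### BP exacerbations depend on baseline BP by construction, but the negative binomial rate model omits it: the rate ratio is valid yet somewhat less precise than it could be

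*SAP*

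**What the plan says.** Section 10.6.4.2 defines the event: "BP exacerbations will be defined as (≥ 25 mmHg increase from baseline or SBP ≥ 180 mmHg", and continues with "DBP ≥ 15 mmHg increase from baseline or DBP ≥ 110 mmHg". Two of these four criteria are relative to the subject's own baseline and two are absolute. On-treatment readings count, scheduled or unscheduled, and post-dialysis values are used by default for in-clinic dialysis. Subjects without a baseline value can still have events through the absolute thresholds.

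Section 8.2.2.2 (Blood Pressure, Model Specification) compares the rates with "a negative binomial model with treatment and the prognostic randomization strata as covariates and the logarithm of time on-treatment as an offset variable". Baseline BP is not among the terms.

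The same section does use baseline BP in its other two models. The Week 52 MMRM includes "baseline BP parameter and the baseline BP parameter by time and treatment by time interaction terms". The end-of-treatment ANCOVA includes "treatment, prognostic randomization stratification factors (see Section 10.10.2) and the corresponding baseline BP parameter".

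The covariate table in Section 10.10.1 describes baseline post-dialysis SBP as "Continuous covariate for change from baseline in SBP analysis, summary statistics of continuous values", with parallel entries for DBP and MAP. It does not mention exacerbations. No other section adds baseline BP to the rate model or explains why it is absent.

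**The concern.** Baseline BP drives this count in both directions. A low baseline reading makes a rise of 25/15 mmHg easier to reach. A high one makes 180/110 mmHg easier, and a fall from 200 to 182 mmHg still counts as an event.

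Measurement noise adds to this. Under Section 10.5.2.1 the post-dialysis baseline for in-clinic hemodialysis is usually the Week -4 value, and the schedule in Section 10.2.1.1 has a single reading at that visit (triplicate on Day 1). A reading that is low by chance lowers the bar for that subject at every later visit. Without a baseline term, all of this between-subject variation goes into the dispersion parameter and widens the interval for the rate ratio.

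The endpoint has some weight. It is a named secondary endpoint, worsening of hypertension is an adverse event of special interest, and Section 10.14.1.1 withdraws statistical testing from the ABPM sub-study. The between-arm inference on BP therefore rests on the clinic readings.

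**Working it through.** **The plan's own figure.** There is none to reproduce. For this endpoint the SAP gives no sample size, event rate, BP mean or SD, or dispersion. The size of the effect can only be simulated under assumed values.

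**Models compared.** All have the form log E(count) = log(time) + intercept + treatment + further terms, with negative binomial variance:
- (a) no baseline BP;
- (b) plus linear baseline SBP and DBP;
- (c) plus linear and squared baseline SBP and DBP.

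**Main simulation.** Inputs from the SAP: the event rule of Section 10.6.4.2 and 1:1 allocation. Assumed: 3,000 subjects, no treatment effect, 4 to 24 visits each with log(visits) as offset, DBP mean 75 with SDs 10 (between) and 9 (within), and the SBP values below. The strata were left out of all three models. Results are means of four replicates.

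| SBP mean; SD between/within; drift SD; baseline readings | SE (a) | SE (b) | SE (c) | Correlation of baseline SBP with event rate |
|---|---|---|---|---|
| 135; 15/15; 0; 1 | 0.0456 | 0.0402 | 0.0399 | -0.44 |
| 135; 15/15; 8; 1 | 0.0483 | 0.0443 | 0.0439 | -0.40 |
| 140; 20/15; 8; 1 | 0.0455 | 0.0442 | 0.0428 | -0.17 |
| 150; 22/15; 8; 1 | 0.0418 | 0.0410 | 0.0388 | 0.08 |
| 140; 20/12; 10; 3 | 0.0518 | 0.0509 | 0.0496 | 0.15 |
| 135; 20/10; 12; 1 | 0.0572 | 0.0550 | 0.0539 | -0.05 |
| 160; 20/15; 8; 1 | 0.0381 | 0.0369 | 0.0353 | 0.23 |

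Reduction in SE = 1 - SE(adjusted)/SE(a).
- Linear terms: smallest 1 - 0.0509/0.0518 = 1.7%, largest 1 - 0.0402/0.0456 = 11.8%.
- With squared terms: smallest 1 - 0.0496/0.0518 = 4.2%, largest 1 - 0.0399/0.0456 = 12.5%.
- In variance, 3 to 22% for linear terms and 8 to 23% with squared terms. The latter is roughly what 1/(1 - 0.0817) = 1.09 to 1/(1 - 0.233) = 1.30 times as many subjects would give.

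The correlation changes sign across scenarios because the two kinds of criterion pull in opposite directions. That is why a linear term alone can gain little, and why squared terms give the more reliable gain.

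**Second simulation.** This used 1,000 subjects per arm, 0.1 to 3.5 years on treatment and the SAP visit grid. Assumed SBP: mean 138-148, SD 20 between and 13-21 within. Assumed DBP: mean 74-78, SD 10 between and 7-11 within. The variance without baseline was 1.02 to 1.18 times that with linear terms, and 1.13 to 1.25 times that with squared terms added. As SE reductions, 1 - 1/√1.02 = 1% to 1 - 1/√1.18 = 8%, and 1 - 1/√1.13 = 6% to 1 - 1/√1.25 = 11%. The base case gave SEs of 0.0514, 0.0492 and 0.0474.

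**On the interval.** In that base case at a rate ratio of 1, exp(±1.96 × 0.0514) gives 0.904 to 1.106, and exp(±1.96 × 0.0474) gives 0.911 to 1.097.

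**The case against.** The strongest reply is that nothing here is wrong. In a 1:1 randomized trial, a rate model adjusted for the stratification factors gives a valid comparison. A reader might infer bias from the fact that events are defined against baseline, but the dependence is the same in both arms on average. This objection stands and limits the point to precision.

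A reader might also see the rate model as a lone inconsistency. The documents do not support that. Hemoglobin responders (CMH) and percent time in range (van Elteren) are analyzed in Section 8.1.2.2 without baseline hemoglobin. MACE in Section 7.2.2 uses treatment, dialysis type and region. The events of special interest in Section 8.2.4 are compared by CMH. The plan tends to give baseline values to change-from-baseline models and not to event analyses. The one further BP model, "an ANCOVA with terms for treatment and baseline 24-hour average SBP" for the ABPM sub-study, is also a change-from-baseline model and will no longer be tested.

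The gain is small, and assumed: about 0.01 at each end of the interval in the base case above. Nor is baseline BP shown to be the strongest available predictor, since no other predictor was compared. High-baseline cases such as 200 to 182 mmHg are already visible, because Section 10.6.4.2 splits events at 180 and 110 mmHg by whether baseline was below the threshold.

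Finally, adjustment has a side effect. Section 8.2.2.2 also reports model-estimated rates per arm. With squared terms and a log link, rates evaluated at average covariates fall below the observed ones: in one simulation under assumed values, 0.246 per visit against 0.262 crude, about 6% lower. That stands, and the fix has to deal with it.

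**Conclusion.** The point holds as a minor matter of efficiency. The count depends on baseline BP by construction, the trial already collects that value, and the rate model does not use it. Both simulations agree in direction in every scenario. Across the seven main scenarios the standard error of the log rate ratio falls by about 2 to 12%, or about 4 to 12% when non-linearity is allowed; in the second simulation linear terms alone gained as little as 1%. These sizes rest entirely on assumed BP distributions and could differ in the trial's data.

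The planned rate ratio is neither biased nor invalid. With a log link, and a treatment rate ratio that is constant across baseline BP, adjustment leaves the quantity being estimated unchanged. The endpoint is secondary, without multiplicity control, and tested only for nominal significance, so no primary conclusion depends on it.

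**What to change.** In the exacerbation rate model of Section 8.2.2.2:
- Add baseline SBP and baseline DBP, each as a linear and a squared term. Use the same pre- or post-dialysis baseline that defines the event in that display.
- Keep subjects with missing baseline BP through a missing-baseline indicator, since Section 10.6.4.2 allows them to have events.
- Report the per-arm rates per 100 patient-years as rates standardized over the observed baseline distribution, so that they stay comparable with the crude rates shown beside them.

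The cost is a few sentences of SAP text, four model terms plus the indicator, and one standardization step. No new data are needed. The missing-baseline rule and the standardization are the real downsides, and both should be written down before unblinding.

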 To compare daprodustat to rhE the symptom severity and chan 	PO on • Change from Baseline at Wk 8,12, 28, 52 in PGI-S
Exploratory Objectives	Exploratory Endpoints (statistical testing not planned)
 To further compare daprodustation rhEPO on Hgb variability 	 Hgb observed and change from baseline across all visits to end of treatment % of time Hgb is above, within and below the range of

Objectives	Endpoints
Objectives	 Endpoints 10-11.5 g/dL during EP and MP Number (%) of subjects with mean Hgb above, within and below the Hgb analysis range during EP and at the end of treatment Number (%) of subjects with a Hgb <7.5 g/dL during the EP and MP Number of times Hgb < 7.5 g/dL during the EP and MP Number (%) of subjects with a >1g/dL increase in Hgb over 2 weeks (assessed at Week 2 and Week 4) or a >2 g/dL increase in Hgb within any 4 week period from Week 4 to Week 52 Number (%) of subjects with a >1g/dL decrease in Hgb over 2 weeks (assessed at Week 2 and Week 4) or a >2 g/dL decrease in Hgb within any 4 week period from Week 4 to Week 52 Number (%) of subjects with a >1g/dL decrease in Hgb over 2 weeks (assessed at Week 2 and Week 4) or a >2 g/dL decrease in Hgb within any 4 week period from Week 4 to Week 52 N (%) of subjects with a Hgb value ≥ 12 g/dL during the EP and MP Number of times Hgb ≥ 12 g/dL during the EP and MP
To compare daprodustat to rhEPO on measures of iron parameters	 % of time Hgb ≥ 12 g/dL during the EP and MP Observed and change from baseline in hepcidin, ferritin, TSAT, total iron, TIBC across all visits to end of treatment Average quarterly ferritin Average quarterly TSAT Average quarterly IV iron dose/subject N (%) of subject who met iron management criteria N (%) of subjects who reduced IV iron supplementation relative to baseline (defined as total iron (mg) over 4 weeks prior to randomization) during EP (defined as average monthly IV iron dose (mg) over Weeks 28 to 52)
To further compare daprodustat to rhEPO on BP and BP medication changes	 Observed and change from baseline in SBP, DBP and MAP by visit Number of BP medications per subject by visit Change from baseline in the number of BP medications per subject by visit N (%) of subjects who had no change, an increase or a decrease in the dosage or number of BP medications from baseline by visit

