8.2.3.2. Planned Exploratory Safety Display Details

Blood Pressure

The last on-treatment BP parameter change from baseline value (SBP, DBP, and MAP) recorded prior to the first change in BP medications will be summarized using mean, standard deviation, minimum, P25, median, P75, and maximum by treatment group. The first change in blood pressure medication occurs at the earliest time a new anti-hypertensive medication is administered or if the dose or frequency of an existing blood pressure medication is changed for any reason (increased, decreased, discontinued, or switched to another agent) in any anti-hypertensive medication, except medication records with frequencies of "Once only" and "PRN."

Number of BP medications per subject while the subject was on treatment will be summarized using mean, standard deviation, minimum, P25, median, P75, and maximum for each scheduled visit by treatment group. Number of BP medications for each subject at baseline is defined as the number of medications taken on the day before randomized treatment start date. For end of treatment, it is defined as the number of medications taken on last non-zero dose date + 1 day. The number of BP medications at all other nominal visits is defined as the number of medications taken on the day of the visit. Medication records with frequencies of "Once only" and "PRN" will be excluded from this summary.

Change from baseline in the number of BP medications per subject while the subject was on treatment will be summarized using mean, standard deviation, minimum, P25, median, P75, and maximum for each scheduled visit by treatment group. The number of BP medications at baseline, end of treatment and all other nominal visits will be defined as described in the previous paragraph. Medication records with frequencies of "Once only" and "PRN" will be excluded from this summary.

Additionally, the number and percentage of subjects who had no change, at least one change, an increase, a decrease or a switch in the dosage or number of BP medications from baseline while the subject was on treatment will be summarized for each scheduled post-baseline visit by treatment group (see Section 10.6.4 for details of classifying BP medication changes). Medication records with frequencies of "Once only" and "PRN" will be excluded from this summary.

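### The BP-medication rule counts a one-for-one switch under Increase as well as Switch, and its categories show ever-changed status rather than change from baseline at the visit

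*SAP*

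**What the plan says.** Section 2.2 lists an exploratory endpoint, with no statistical testing planned: the number and percentage of "subjects who had no change, an increase or a decrease in the dosage or number of BP medications from baseline by visit".

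Section 8.2.3.2 plans the display at each scheduled post-baseline visit while on treatment, for "subjects who had no change, at least one change, an increase, a decrease or a switch". It leaves out once-only and as-needed records and refers to Section 10.6.4 for the classification.

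Section 10.6.4.2 gives the rules:

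- No change requires "no new anti-hypertensive records since baseline" and no change to existing records up to the visit.
- Increase is the "addition of new anti-hypertensive records for any reason", or a change whose recorded reason is an increase.
- Decrease is the "discontinuation of an anti-hypertensive record with primary reason for change" showing discontinuation, or a change whose recorded reason is a decrease.
- Switch is a "change with a reason of 'switched to another agent' since baseline until date of visit".

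Increase, Decrease and Switch all run from baseline to the visit date, and No change covers the same interval. Neither section says whether the categories are exclusive or which takes precedence.

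**The concern.** The endpoint asks whether dosage or number of BP medications has gone up or down relative to baseline at a visit. The rule asks whether any new record has appeared since baseline. The two differ in ordinary situations. A replacement agent needs a new record, so a switch also enters Increase. An agent added and later withdrawn leaves the subject in Increase for good.

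The table is meant to help interpret the blood pressure results. The background in Section 10.14 says that BP elevation under ESAs often leads to more antihypertensive treatment, and Section 10.6.4.3 makes worsening of hypertension an adverse event of special interest. Section 10.14.1.2 marks the corresponding sub-study comparison of antihypertensive changes as not done, so the main-study displays are what remain for the direction of change. If switching differed between arms, part of a difference in the Increase column would reflect switching and not added treatment.

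**Working it through.** There is no figure in the plan to reproduce: no sample size, power or event rate bears on this point. The check applies the Section 10.6.4.2 rules literally to constructed medication histories and compares the result with the visit-day count of BP medications in Section 8.2.3.2.

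**Inputs.** Rules as set out in Section 10.6.4.2. Change in count = medications taken on the visit day minus medications at baseline (Section 8.2.3.2). Visit days: Week 4 = 4 × 7 = 28; Week 8 = 56; Week 16 = 112; Week 28 = 196; Week 52 = 364. The histories are invented for illustration. In each, drug A is taken at baseline, so the baseline count is 1.

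**(a) One-for-one switch.** A stopped on day 50 with the switch reason; B started on day 51.
**(b) Added, then withdrawn.** A continues; B started on day 30 and discontinued on day 60.
**(c) Dose reduction of A on day 50,** assuming that the eCRF closes the old record and opens a new one at the lower dose.

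| History | Week 4 | Week 8 | Weeks 16, 28, 52 |
|---|---|---|---|
| (a) category | No change | Increase, Switch | Increase, Switch |
| (a) change in count | 0 | 1 − 1 = 0 | 0 |
| (b) category | No change | Increase | Increase, Decrease |
| (b) change in count | 0 | 2 − 1 = +1 | 1 − 1 = 0 |
| (c) category | No change | Increase, Decrease | Increase, Decrease |
| (c) change in count | 0 | 0 | 0 |

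**Reading.**

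1. In (a), B's new record meets the first limb of Increase, and A's stop reason meets Switch. No clause removes B's record from Increase. The number of agents has not changed, so the classification and the adjacent count display disagree by construction.
2. In (b), Week 8 is right. From Week 16 the regimen is the baseline one, yet the subject remains in Increase and Decrease and cannot return to No change.
3. Result (c) holds only under the stated assumption about the eCRF. Results (a) and (b) do not need it.

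**The case against.** The strongest reply is that the rules are explicit and reproducible, and that a switch is not lost: it has its own category, shown beside the others. The display also has a column for at least one change, which suggests that the direction columns were never meant to be exclusive. This stands. A reader might infer that switches are reported as treatment intensification in place of switches. The text supports only double counting.

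A reader might also infer that every dose reduction is counted as an Increase. The SAP does not show the eCRF layout, and its wording points the other way. Increase has a separate limb for changes recorded as increases, which would be largely redundant if each dose change opened a new record. Section 8.2.3.2 likewise separates a new medication from a changed dose or frequency of an existing one. That extension is only conditional.

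Third, net change in number is not hidden. Section 8.2.3.2 plans the number of BP medications by visit and its change from baseline, both counted on the visit day. This stands for number. Those displays do not show net dosage.

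Fourth, accumulation is partly a design choice, and an ever-changed table by visit differs from the separate summary of cumulative changes to Week 52 and end of treatment. That is fair, but it does not make the table match an endpoint worded as change from baseline by visit. Nor does it follow that the reported percentage can only rise: the individual's status is permanent, but the table covers on-treatment time only, so the contributing subjects vary.

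**Conclusion.** The point holds in a limited form and is minor. Under the rule as written, a one-for-one switch is counted under both Switch and Increase. This inflates the Increase column relative to an endpoint defined by dosage or number, and disagrees with the visit-day count. The categories also describe ever-changed status and not the regimen at the visit compared with baseline. Both conclusions follow from the wording alone, on the premise that a replacement agent is entered as a new record.

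The size of the inflation cannot be computed, and any percentage would be an assumption. A reader might infer that the plan's main BP conclusions are at risk; the document does not support that. The endpoint is exploratory, descriptive and untested. The co-primary analyses and the multiplicity-controlled tests do not use it, and the secondary BP analyses in Section 8.2.2.2 (models of BP values and exacerbation rates) do not use this classification.

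**What to change.** In Section 10.6.4.2:

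1. Exclude from Increase any new record that replaces an agent stopped with the switch reason. If the eCRF opens a new record on a dose reduction, also exclude a record that continues the same agent at a reduced dose.
2. State that a subject may fall in more than one category, or give a precedence. This is needed under any definition, since one agent can be added while another is lowered.
3. Either classify by comparing the visit-day regimen with the baseline regimen, or keep the present interval and label the table 'ever since baseline'.

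The cost is a few lines of SAP wording and reprogramming of one exploratory table. The rules already rely on recorded medication dates and change reasons, so items 1 and 2 need no new data collection.
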